15.3.3. Secondary Efficacy Endpoint LDL-C

For this study, the directly measured LDL-C value is used when available, otherwise the calculated LDL-C value is used. All LDL-C analyses will be presented in both the conventional unit (mg/dL) and the standardized (SI) unit (mmol/L).

Percent change from baseline in LDL-C at Month 6 will be analyzed using a linear model with percent change from baseline as response, treatment group and baseline LDL-C as covariates. Since the variances of the response are potentially different for the two treatment groups (more variable with active treatment), the model will allow different residual variances by treatment group. Specifically, PROC MIXED can be used with ‘REPEATED / group = trt’ statement. In addition, Kenward-Roger method is to be used for approximating the degrees of freedom (‘DDFM=kenwardroger’ option to MODEL statement). Fitted mean (Least Square or LS means) percent changes from baseline for each treatment group will be calculated (with 95% CI) at baseline LDL-C level of 140 mg/dL. The estimated difference in percent changes from baseline between treatment groups will be provided with 95% CI and p-value for testing of no difference.

Since patients with missing LDL-C at Month 6 may have underlying distributions depending on whether the patient was assigned to the active treatment and remained on active treatment at the time, a pattern mixture model (PMM) is used for the analysis, using a multiple imputation approach. Specifically, missing LDL-C values at Month 6 were simulated using a linear regression model with Month 6 LDL-C value as response, and covariates including baseline LDL-C value, and an indicator variable that equals 1 if and only if the patient was assigned to the active treatment and remained on treatment at Month 6 (Day 182) (this can be achieved using PROC MI with monotone regression). Simulated datasets (20 replicates) are analyzed as described previously and the resulted estimates are combined using Rubin’s method (Rubin, 1987; PROC MIANALYZE).

For tertiary endpoints of LDL-C measured at all timepoints (Baseline, Month 3, 6, 12, 18, 24, 30, 36, 42, 48, 54, and 60), the observed values at each timepoint, changes from baseline, and percent changes from baseline will be summarized by treatment groups. Differences of the

changes from baseline, and percent changes from baseline between the treatment groups will be presented together with 95% CIs at each timepoint, as descriptive analyses with no imputation.

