10.6.5. Treatment Month 3 (Visit T3; ± 5 days)

Patients will undergo the following assessments and procedures at Month 3 (Visit T3):

- Concomitant medication review (ongoing)
- Assess AEs, SAEs, and potential clinical endpoints
- Weight
- Vital signs

- Central clinical laboratory evaluations:
 - Hematology, blood chemistry, and urinalysis
 - Basic fasting lipids (TC, calculated LDL-C, HDL-C, non-HDL-C, and TGs)
 - HbA_{1C}
- Return of IMP; assessment and recording of IMP adherence
- IWRS contact to obtain new MED ID number for double-blind IMP
- Dispense double-blind IMP and provide dosing and storage instruction
- Diet and exercise counselling
- Schedule next visit

Note: If the patient discontinues at or between study visits, please proceed to Section 10.7 for detailed instructions.

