15.3.4. Secondary Efficacy Endpoint HbA_{1c}

All efficacy analyses of HbA_{1c} will be carried out stratified by the baseline glycemc status in the FAS. The subgroup of patients with Inadequately Controlled Diabetes (ICDM) at baseline is of primary interest. The other subgroups include Diabetes (that includes ICDM as a subset), Prediabetes, Normoglycemic, and No Diabetes (Prediabetes and Normoglycemic combined).

Analysis for the change from baseline to Month 12 in HbA_{1c} will be analyzed similarly as LDL-C, with change from baseline as response, treatment group and baseline HbA_{1c} as covariates. There is no need to specify variance heterogeneity (no 'REPEATED' statement) and the default method for degrees of freedom calculation can be used. Fitted mean (LS means) changes from baseline for each treatment group will be calculated (with 95% CI) at baseline HbA_{1c} levels of 8% and 7% for ICDM and Diabetes, 6% for Pre-Diabetes and 5.5% for Normoglycemic and the combined No Diabetes groups. The estimated differences in changes from baseline between treatment groups will be provided with 95% CIs and p-values for testing of no difference.

Missing HbA_{1c} data at Month 12 will also be handled using PMM based on whether the patient was still on treatment at Month 12 (Day 365), similar to LDL-C above.

For tertiary endpoints of HbA_{1c} measured at all timepoints (Baseline, Month 3, 6, 12, 18, 24, 30, 36, 42, 48, 54, and 60), the observed values at each timepoint, and changes from baseline will be summarized by treatment groups. Differences of the changes from baseline between the treatment groups will be presented together with 95% CIs at each timepoint, as descriptive analyses with no imputation.

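### The imputation models named for Month 6 LDL-C and Month 12 HbA1c leave out the patient's own earlier values, so both estimates can be biased if missingness tracks early response differently by arm

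*SAP*

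**What the plan says.** For LDL-C, SAP 15.3.3 states that "missing LDL-C values at Month 6 were simulated using a linear regression model with Month 6 LDL-C value as response". The predictors it names are "covariates including baseline LDL-C value, and an indicator variable that equals 1 if and only if the patient was assigned" to active drug and was still on it at Day 182. An active patient who has stopped drug is thus grouped with placebo. The SAP adds that "this can be achieved using PROC MI with monotone regression", and combines 20 replicates by Rubin's method. The analysed endpoint is percent change from baseline.

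For HbA1c, SAP 15.3.4 says that missing Month 12 data "will also be handled using PMM based on whether the patient was still on treatment at Month 12 (Day 365), similar to LDL-C above". The endpoint there is absolute change.

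Protocol 15.7.2 makes the pattern mixture model the primary handling for both endpoints, with observed cases as supportive. Earlier values exist: the Month 3 visit (Protocol 10.6.5) includes "Basic fasting lipids (TC, calculated LDL-C, HDL-C, non-HDL-C, and TGs" and HbA1c, and the Month 6 visit (Protocol 10.6.6) includes HbA1c again.

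Protocol 15.7.3 has a repeated-measures model, but for tertiary endpoints. The SAP, which takes precedence (Protocol 15.1), gives by-visit descriptive summaries without imputation instead. Both endpoints lie outside the testing hierarchy (SAP 8.3).

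**The concern.** Given the named predictors, a patient still on drug who misses Month 6 is imputed as an average on-drug patient with that baseline, whatever Month 3 showed. The data are then treated as missing at random given baseline and drug status alone. If poor early responders miss the later visit more often in one arm than in the other, the difference between arms shifts.

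The observed-case analysis rests on the same assumption, so close agreement between the two would reassure wrongly. Missing samples are plausible: visits could become remote (Protocol 10.6.6, 10.6.8), lipid samples are not drawn unless the patient has fasted (Protocol 11.4), and local laboratory results are not analysed (SAP 16.3).

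A second, smaller issue concerns LDL-C alone. A regression in mg/dL with one additive drug indicator assumes the same mg/dL fall at every baseline, whereas the endpoint is a percentage.

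**Working it through.** **Plan figures.** The documents give no sample size, power or visit-level missing rate for either endpoint, so there is no figure to reproduce. The 1% per year loss to follow-up is a study-level rate. Everything below rests on stated assumptions.

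**First-order size.** Let g be the log odds ratio of being missing per SD of the earlier-visit residual, p the missing fraction, ρ the correlation between visit residuals and σ the residual SD. Among observed patients the earlier residual averages about −g·p SD, so the later mean moves by about −ρσgp. Imputing from those patients on baseline and drug status copies the shift:

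bias in the difference ≈ −ρσ(p_A·g_A − p_P·g_P), where A is active and P is placebo.

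- HbA1c, assuming ρ = 0.7, σ = 0.9, odds ratio 1.5 in the active arm only (g = 0.405), p = 0.10: −0.7 × 0.9 × 0.405 × 0.10 = −0.026.
- LDL-C, assuming ρ = 0.6, σ = 25 mg/dL, same g and p: −0.6 × 25 × 0.405 × 0.10 = −0.61 mg/dL; over a baseline of 140 mg/dL this is −0.43 points.
- With equal g and equal p in both arms the two terms cancel.

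**Simulation.** LDL-C: 14,000 patients, baseline mean 140 and SD 30, 20% effect on drug, 10% off drug. HbA1c: 3,000 patients, effect −0.10 on drug, 12% off drug, one earlier visit. Correlations and residual SDs are as above, with 20 imputations. Bias is measured against the full-data estimate (about −18 points and about −0.09), at 5% / 10% / 20% missing in each arm.

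| Missingness by early response | LDL-C bias (points) | HbA1c bias |
|---|---|---|
| Unrelated | −0.06 / −0.08 / −0.21 | 0.000 |
| OR 1.5 per SD, both arms | −0.07 / −0.04 / −0.16 | within 0.001 |
| OR 1.5, active only | −0.24 / −0.49 / −1.00 | −0.013 / −0.024 / −0.046 |
| OR 2 active, 0.5 placebo (extreme) | −0.79 / −1.53 / −3.00 | −0.043 / −0.083 / −0.155 |

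Standard errors under the SAP model were 0.34–0.37 points and 0.034–0.037. In the active-only row at 20% missing, the bias is 1.00/0.364 = 2.7 SE for LDL-C and 0.046/0.037 = 1.2 SE for HbA1c. In the same row at 10%, HbA1c was −0.083 with full data, −0.108 in observed cases and −0.108 under the SAP model. Observed cases would not expose the error.

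A second simulation, with odds ratio 1.65 per SD in the active arm only and 8% / 15% missing, gave LDL-C −0.63 / −1.14. For HbA1c (1,200 per arm), with placebo patients whose HbA1c had risen more often missing, it gave +0.026 and +0.050 at its two missing rates, towards the null. The sign is therefore not fixed. A third gave LDL-C −0.4 to −0.9 when dependence differed by arm.

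**Scale mismatch.** A 20% effect at 140 mg/dL is 28 mg/dL. Applied to everyone, its mean percentage is about 20 × [1 + (30/140)²] = 20.9%, an excess of 0.9 points among imputed on-drug patients. With 10% missing and 90% on drug: 0.9 × 0.10 × 0.9 ≈ 0.08, matching the first row. The second simulation gave −0.10 / −0.17 at 8% / 15% missing.

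**Does adding the earlier value cure it?** In the first simulation, bias fell to at most 0.1 point (LDL-C) and 0.003 (HbA1c). There, however, off-drug patients were off drug at both visits. If a patient stops between Months 3 and 6 and the model holds only a Month 6 indicator, the treated Month 3 value is carried forward by about ρ × effect = 0.6 × 20 = 12 points. A simulation with 8–12% off drug, 30–60% of these stopping after Month 3, and 40–50% of off-drug values missing put such patients 11–12 points too low. Overall bias was −0.13 to −0.46, against −0.03 to −0.04 under the SAP. A further one gave −0.19 to −0.33 against −0.05 to −0.08 under the SAP; adding a Month 3 on-drug indicator brought bias within 0.04 points in every scenario.

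**The case against.** A reader might infer that the models use nothing but these two predictors and that both estimates are biased. The documents support neither. The SAP's list is introduced as including those covariates, so it is not clearly closed, and the HbA1c model is given only by reference. Nothing in the documents reports a missing rate or a link between missingness and response.

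The trial is double-blind. Post-randomization LDL-C is masked to site and patient (Protocol 8.3, SAP 4.2), and the first LDL-C alert comes at Month 6 (Protocol 12.1.6.3.3), so nobody can act on a poor Month 3 LDL-C; a link would have to run through adherence or tolerability. The obvious arm-specific route, stopping drug, is what the indicator captures. Wide windows (Days 137–273 and 274–456, SAP Appendix 3) and the use of unscheduled visits limit missingness. Blinded sites should also react alike to a rising HbA1c in either arm, which is the near-nil case.

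Most of this stands, and it limits the point to a conditional one. It bears less on HbA1c, which is not in the masked list. The near-nil result was also obtained with equal missing rates; by the formula above, equal dependence with unequal rates does not cancel.

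SAP 15.4.4, on additional diabetes analyses, is listed in the contents but its text was not available, so a further HbA1c sensitivity analysis there cannot be ruled out. The on-treatment and pre-cross-in analyses (SAP 15.4.2, 15.4.3) summarise observed values and do not use earlier visits to handle missing ones.

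**Conclusion.** The point holds in conditional form. The named predictors omit earlier values that the trial collects, and no analysis in the available SAP text uses those values to handle the missing ones. Bias arises only if missingness depends on early response differently by arm beyond on-drug status.

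Under the assumed rates it is about 0.2–1.1 points of about 18 for LDL-C, too small to change a conclusion about LDL-C lowering. For HbA1c it is about 0.01–0.05. Against an assumed effect of −0.09 that is roughly 15% to 50% in the first simulation (0.013/0.09 and 0.046/0.09), which could matter to interpretation. The extreme row of the table is not relied on. The LDL-C scale mismatch is real whatever the dropout pattern, but small at about 0.05–0.2 points.

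It would be wrong to infer any effect on the MACE analyses or on control of type I error. The missing rates, odds ratios, correlations and HbA1c effect are all assumptions.

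**What to change.** Before unblinding, give the complete covariate list in SAP 15.3.3 and 15.3.4 and impute sequentially.

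- LDL-C: Month 3, then Month 6, from baseline, the Month 3 value, and on-active-drug indicators defined separately at Month 3 (Day 91) and Month 6 (Day 182). Work in percent change or log LDL-C, or add indicator-by-baseline terms.
- HbA1c: Month 3, then 6, then 12, in the same way, with an indicator at each visit (Days 91, 182 and 365).
- Use fully conditional specification for the non-monotone cases, such as Month 3 missing but Month 6 present.
- Keep the 20 replicates and Rubin's rule, and report missingness by arm and on-drug status.

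The visit-specific indicators are essential: adding earlier values with a single indicator at the endpoint visit would replace one bias with another. The cost is slightly more complex imputation code and a few lines of SAP text; no new data are needed.

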15.3.4. Secondary Efficacy Endpoint HbA_{1c}

All efficacy analyses of HbA_{1c} will be carried out stratified by the baseline glycemc status in the FAS. The subgroup of patients with Inadequately Controlled Diabetes (ICDM) at baseline is of primary interest. The other subgroups include Diabetes (that includes ICDM as a subset), Prediabetes, Normoglycemic, and No Diabetes (Prediabetes and Normoglycemic combined).

Analysis for the change from baseline to Month 12 in HbA_{1c} will be analyzed similarly as LDL-C, with change from baseline as response, treatment group and baseline HbA_{1c} as covariates. There is no need to specify variance heterogeneity (no 'REPEATED' statement) and the default method for degrees of freedom calculation can be used. Fitted mean (LS means) changes from baseline for each treatment group will be calculated (with 95% CI) at baseline HbA_{1c} levels of 8% and 7% for ICDM and Diabetes, 6% for Pre-Diabetes and 5.5% for Normoglycemic and the combined No Diabetes groups. The estimated differences in changes from baseline between treatment groups will be provided with 95% CIs and p-values for testing of no difference.

Missing HbA_{1c} data at Month 12 will also be handled using PMM based on whether the patient was still on treatment at Month 12 (Day 365), similar to LDL-C above.

For tertiary endpoints of HbA_{1c} measured at all timepoints (Baseline, Month 3, 6, 12, 18, 24, 30, 36, 42, 48, 54, and 60), the observed values at each timepoint, and changes from baseline will be summarized by treatment groups. Differences of the changes from baseline between the treatment groups will be presented together with 95% CIs at each timepoint, as descriptive analyses with no imputation.

15.3.5. Secondary Efficacy Endpoint hs-CRP

Due to the highly skewed distribution of hs-CRP, a nonparametric analysis based on Wilcoxon rank sum test will be performed for percent change from baseline to Month 6. Hodges-Lehmann estimate of location shift and its 95% CI will be provided. Only observed values will be used with no imputation.

For hs-CRP measured at other timepoints (Month 12, and End-of-Study, which is defined to be the last measurement of each patient), the observed values at each timepoint, and percent changes from baseline will be summarized by treatment groups.

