15.7.2. Secondary Efficacy Lipid and Other Biomarker Endpoints

Percent change from baseline to Month 6 in LDL-C and absolute change from baseline to Month 12 in HbA_{1C} will be analyzed using analysis of covariance (ANCOVA), with treatment group as a factor and the relevant baseline as a covariate. The ANCOVA for LDL-C will be performed in the FAS. The ANCOVA for HbA_{1C} will be performed in the Inadequately Controlled Diabetes Efficacy Population. Two methods for data handling will be used: the first (primary) will involve specification of the missing data mechanism using a pattern mixture model (PMM), while the second (supportive) will be observed case data only. For each analysis, the least squares mean (LSM) and standard error (SE) will be provided for each treatment group, along with the placebo-corrected LSM, its 95% CI, and associated p-value. A nonparametric analysis based on Wilcoxon rank sum test and Hodges-Lehmann (H-L) estimate of location shift will be performed in FAS for percent change from baseline to Month 6 in hs-CRP. No imputation will be performed for the hs-CRP endpoint due to the extreme skewed distribution.

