7.2.3. Baseline

For safety parameters, unless otherwise specified, baseline is defined as the last non-missing measurement taken on or prior to Day 1 (including unscheduled assessments).

Baseline for fasting glucose is defined as the mean of the last two non-missing fasting values measured on or prior to Day 1. If only one value is available, then that single value will be used as baseline. Baseline HbA_{1C} is defined as the last non-missing value on or prior to Day 1.

Baseline for lipids parameters (LDL-C, non-HDL-C, TC, HDL-C, TG) is defined as the mean of the last two non-missing fasting values measured on or prior to the *date of randomization*. If only one value is available, then that single value will be used as baseline. If the patient had no fasting values available at baseline, non-fasting values will be used.

Baseline for hs-CRP is defined as the last non-missing value on or prior to the date of randomization.

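### The Month 6 hs-CRP test does not adjust for baseline, unlike the LDL-C and HbA1c analyses; a baseline-adjusted rank test of the same endpoint would be more precise at little cost

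*SAP*

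**What the plan says.** Percent change in hs-CRP to Month 6 is a secondary biomarker endpoint in both documents. SAP 15.3.5 gives the reason for a rank method, "Due to the highly skewed distribution of hs-CRP", and then the method: "a nonparametric analysis based on Wilcoxon rank sum test will be performed for percent change from baseline to Month 6". The effect measure follows: "Hodges-Lehmann estimate of location shift and its 95% CI will be provided". On missing data it says "Only observed values will be used with no imputation". Protocol 15.7.2 plans the same test and estimate.

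Neither document names a covariate or stratum for this test. The other two secondary biomarker endpoints are adjusted. SAP 15.3.3 models LDL-C with "treatment group and baseline LDL-C as covariates", and SAP 15.3.4 models HbA1c with "treatment group and baseline HbA_{1c} as covariates".

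The baseline needed is available. SAP 7.2.3 states "Baseline for hs-CRP is defined as the last non-missing value on or prior to the date of randomization", and the schedule of events collects hs-CRP at T1.

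hs-CRP lies outside the seven-step testing hierarchy. Protocol 15.7 treats such p-values as nominal, and SAP 8.3 treats them as informational.

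**The concern.** Percent change is a monotone function of log(Month 6) minus log(baseline). A Wilcoxon test on percent change is therefore the same test as a Wilcoxon test on the log ratio. Baseline is used, but with its slope fixed at 1 and not estimated. When the correlation between the two visits is below 1, patients with a high baseline tend to fall and those with a low baseline tend to rise. That predictable movement stays in the ranks as noise. Adjusting for baseline removes it, as the plan already does for LDL-C and HbA1c.

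The effect measure has a related weakness. A location shift is a constant difference in percentage points. If the drug multiplies hs-CRP by a constant, no constant shift exists, and the estimate mixes the drug effect with the variability of the log ratio.

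At stake are the precision and readability of one secondary biomarker result, not the validity of any test.

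**Working it through.** **Inputs from the documents.** Wilcoxon test on percent change, no covariate (SAP 15.3.5); about 7000 patients per arm, 1:1; two-sided 0.05. The plan states no effect size, SD, correlation or power for hs-CRP, so it has no figure of its own to reproduce on this point. The 1620 events concern the primary endpoint only.

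**Assumptions.** Log-normal hs-CRP with equal SD sigma at both visits; sigma 1.0 to 1.2; rho 0.3 to 0.9 for efficiency and 0.3 to 0.7 for power; 5000 to 7000 patients per arm with a Month 6 value.

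**1. Loss against a baseline-adjusted rank test of the same endpoint.** The size of the correlation between the log ratio and log baseline is r = sqrt((1 − rho)/2); its sign is negative. For normal variables the rank correlation is r_S = (6/π) × arcsin(r/2). Randomization makes baseline independent of treatment, so adjustment leaves the expected treatment effect on the ranks unchanged and multiplies their residual variance by 1 − r_S². That factor is the efficiency of the planned test.

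| rho | r | r_S | Efficiency of planned test |
|---|---|---|---|
| 0.3 | 0.592 | 0.574 | 0.67 |
| 0.5 | 0.500 | 0.483 | 0.77 |
| 0.7 | 0.387 | 0.372 | 0.86 |
| 0.9 | 0.224 | 0.214 | 0.95 |

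Since 1/0.67 = 1.49 and 1/0.95 = 1.05, adjustment is worth about 5% to 49% more patients. Simulation (3000 per arm, log SD 1.1) agreed with the 0.67 to 0.95 range. The adjusted test was ahead at every rho from 0.3 to 0.9, also with acute-phase spikes added.

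**2. Comparison with log-scale ANCOVA.** The variance ratio of ANCOVA to the unadjusted change is (1 + rho)/2. Multiplied by the Wilcoxon efficiency 3/π = 0.955, this gives 0.62, 0.72, 0.81 and 0.91 at rho 0.3, 0.5, 0.7 and 0.9. This advantage is not robust. With an assumed 5% of acute-phase spikes at each visit, simulated efficiency of the planned test was 0.65, 0.75, 1.00 and 1.27 at rho 0.3, 0.5, 0.7 and 0.8.

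**3. Power of the planned test.** The effective SD is sigma × sqrt(2(1 − rho)) / sqrt(3/π). In the least favourable case (5000 per arm, sigma 1.2, rho 0.3):
- SD = 1.2 × sqrt(1.4) / 0.977 = 1.453
- SE = 1.453 × sqrt(2/5000) = 0.0291
- 10% reduction: z = 0.1054/0.0291 = 3.63, power Φ(3.63 − 1.96) = 95%
- 5% reduction: z = 0.0513/0.0291 = 1.77, power 42%

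Over the whole grid, power is 95% to 100% for a 10% reduction, 100% for 20%, and 42% to 97% for 5%. In the same least favourable case, adjustment raises z for a 5% reduction to 1.77/sqrt(0.67) = 2.16, which is power of about 58%.

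**4. Hodges-Lehmann shift.** Suppose the true effect is a 20% lower ratio in every patient. The simulated shift is −18.8, −16.5 and −15.1 percentage points when the SD of the log ratio is 0.5, 0.9 and 1.1. Since that SD is sigma × sqrt(2(1 − rho)), at sigma 1.1 these spreads correspond to rho of about 0.90, 0.67 and 0.50. The same drug effect gives a different reported number.

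**The case against.** The best defence is that the plan is deliberate, consistent across both documents and safe. A rank test suits a very skewed marker with acute spikes, randomization makes it valid without covariates, and its p-value is nominal. With thousands of patients per arm, only a reduction near 5% could be missed. All of this stands and limits the point to precision.

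A reader might infer four stronger things, none of which the documents support.
- **That baseline is thrown away.** It is not: every patient's baseline is the denominator of percent change. Only the gain from estimating its slope is lost.
- **That a known share of the information is wasted, such as a fifth to a third.** Against log-scale ANCOVA, that range needs rho of about 0.68 down to 0.40. The documents give no rho, and under spikes the loss can vanish or reverse.
- **That the shift cannot be interpreted.** The Hodges-Lehmann estimate is the median of all between-arm differences, defined whether or not a constant shift holds. Its weakness is dependence on spread.
- **That the observed-case rule must change too.** The protocol gives its reason, "No imputation will be performed for the hs-CRP endpoint due to the extreme skewed distribution". A log transform would weaken that reason, but no missing fraction or bias can be derived from the documents, and the adjustment does not depend on it.

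It is also fair to object that testing Month 6 values in place of percent change would alter the stated endpoint. Ranking Month 6 values adjusted for baseline ranks can lose to the planned test as well: with spikes, the planned test's efficiency against it was 1.09 and 1.52 at rho 0.8 and 0.9. Adjusting the ranks of percent change avoids both problems.

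**Conclusion.** The point holds as a minor improvement. The hs-CRP test is the only one of the three secondary biomarker analyses that does not adjust for baseline. Against a baseline-adjusted rank test of percent change, its efficiency is about 0.67 to 0.95. This assumes log-normal data with log SD 1.1 and rho from 0.3 to 0.9, none of which the documents state. No false-positive risk or bias follows, and power is ample for reductions of 10% or more. The Hodges-Lehmann shift may be reported, but it should not stand alone as the effect measure if the drug effect is multiplicative.

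One limit applies: SAP 15.4.4 and 15.6.2 are listed in the contents, but their text is not in the copy reviewed. A supportive hs-CRP analysis there cannot be excluded.

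**What to change.** In SAP 15.3.5:
- Keep percent change to Month 6 as the endpoint, and test it with rank ANCOVA: ranks of percent change on treatment, adjusted for ranks of baseline hs-CRP.
- Keep the Hodges-Lehmann estimate with its 95% CI.
- Add, as supportive, the geometric mean ratio with 95% CI from ANCOVA of log Month 6 hs-CRP on treatment and log baseline.
- Leave the observed-case rule as it is; this change does not need imputation.

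The cost is a few lines of SAP text, made before unblinding, and a short program; no new data are needed. Protocol 15.7.2 names the Wilcoxon test, but Protocol 15.1 gives the SAP precedence where the two differ. There are two small downsides. The report carries a second effect measure, and the Hodges-Lehmann interval remains unadjusted, so it can disagree with the adjusted p-value near 0.05.
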